## **C Study Objectives**

### ***C1 Study Aims***

Our study aims are as follows:

- 1) Aim 1: Examine uptake (i.e., individuals beginning treatment) of the mobile mental health platform compared to referral to usual care.
- 2) Aim 2: Evaluate the effectiveness of the mobile mental health platform, compared to usual care, in (2a) reducing the number of individuals with mental health disorders (primary outcome); (2b) reducing disorder-specific symptoms (secondary outcome); and (2c) improving quality of life and functioning (secondary outcome).
- 3) Aim 3: (3a) Examine if the mobile intervention changes targets previously found to be associated with outcomes, both transdiagnostic (i.e., decreased dysfunctional cognitions, increased use of CBT skills) and disorder-specific (i.e., reduced avoidance for anxiety, increased behavioral activation for depression, reduced dietary restraint and weight/shape concerns for EDs); (3b) determine if changes in targets are associated with clinical benefit; and (3c; exploratory) identify other putative mediators of change (e.g., early engagement in help services, rapid response), (3d; exploratory) within-mobile program predictors of outcome (e.g., sessions completed), and (3e; exploratory) treatment moderators.
- 4) Aim 4 Evaluate stakeholder-relevant outcomes: (4a) costeffectiveness; (4b) students' academic performance; and (4c) attitudes.

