We also propose several mediators, which fall into: 1) primary intervention targets/mechanisms, considered most essential to outcomes (some of which are transdiagnostic and some disorder-specific; and 2) other mediators—early engagement in services and rapid response. CBT theory posits that the most important ways to change symptoms are by changing cognitions and/or changing behaviors. Thus, our transdiagnostic targets are decreased dysfunctional cognitions and increased use of CBT skills. Empirical support for cognitive changes suggests that they are central to reduction in anxious and depressive symptoms. For EDs, although only a few studies have examined change in cognition, it is worth including given its emphasis in CBT theory. There is evidence that acquisition of CBT skills (e.g., challenging thoughts) is another critical target at least for anxiety and depression. Our disorder-specific, evidence-based targets are as follows: reducing avoidance, associated with changing anxiety; increasing behavioral activation, associated with reducing depressive symptoms; and reducing dietary restraint and weight/shape concerns for reducing EDs. We will examine whether the mHealth platform leads to change in the targets listed above and whether target change is associated with clinical benefit. Use of any potentially helpful services (e.g., Lantern, self-help, face-to-face therapy, medication) is also likely to lead to change, particularly in the first 6 weeks. Thus, while not a specific target of intervention, early engagement in help services is a potential mediator of symptom reduction and will be tested. Rapid response in symptoms, with rapid response usually defined as  $\geq 50\%$  reduction in symptoms occurring within the first 4-6 weeks of treatment, predicts longer-term outcome in anxiety, depression, and EDs and is considered a mediator. Within-mobile program indices will be tested as predictors of outcome, including sessions completed, number of messages sent by user and coach, techniques completed, time spent with the program, and coach personalization (i.e., assessed through users' perception and coding a subset of messages. Finally, data will be used to explore moderators—subgroups for whom further tailoring or more intensive services are needed in future iterations. Moderators exploratory and based on prior work; they are: gender, race/ethnicity, expectancy/credibility, symptom severity, duration of problem, comorbidity, disorder for which the person sought treatment, degree of cognitive distortion, impairment, family income, and motivation.

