Analyses for Aim 3 (targets, other mediators, within-mobile program predictors, moderators). Potential mediators are categorized into three groups: 1) clinical targets (Aim 3a and Aim 3b); 2) early engagement with services (Aim 3c); and 3) early clinical response/rapid response (Aim 3c). We will test for mediation using structural equation models (SEM) with confidence intervals derived from bootstrapping of indirect effects and total effects. We will examine targets and mediators preceding changes in outcomes. To draw more informative and coherent conclusions across the three disorders, we will explore meaningful transdiagnostic clinical targets as well as disorder specific targets. For transdiagnostic mediator outcomes, binary clinical case status and quality of life measures are natural outcome measures, but for symptom outcomes, we will use standardized symptom scores (for transdiagnostic outcomes) and nonstandardized symptoms scores (for disorder-specific outcomes). Moderated mediation (with treatment vs control as the moderator) will be tested by constraining the indirect effect to be equal across treatment and control groups and testing differences in chi-square fit. Any significant misfit caused by specifying the indirect effect of each mediator to be equal suggests that there are significant differences in this mediational path between the treatment and control. All mediational paths between the primary predictor and outcome will be estimated simultaneously to account for any and all interdependence between paths and to ensure these interdependencies do not bias estimation. Note that in applying moderated mediation analyses to both transdiagnostic and disorder-specific targets, we will be simultaneously testing whether the intervention engages the targets (Aim 3a) and whether intervention-induced changes in targets are associated with clinical benefit (Aim 3b). Putative moderators (Aim 3e) will examine interaction terms with time point and random assignment in regressions to identify subgroups that benefit most from treatment, and others for whom additional tailoring may be necessary in future refinements of the delivery model. In cases where moderators are significant, we will then conduct mediator analyses separately by subgroups defined by these moderators, because different intervention effects often imply different mechanisms by which effects are occurring. In moderation models, results will estimate the following fixed effects: 1) main effect of time, treatment condition, and each proposed moderator; 2) two-way interactions between time and treatment condition, treatment condition and each moderator, and time and each moderator; and 3) three way interactions between time, treatment condition, and each moderator. The models will also estimate random effects of time nested within individuals, and intercepts nested within campuses. Within-mobile treatment predictors of change (Aim 3d) will use multilevel models using the fixed effects of maineffects of time, and each within-mobile program predictor, and the interaction between within-mobile program predictors and time estimating random effect of time nested within individuals and intercepts nested within campuses.

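### A significant moderator leads to separate mediation analyses by subgroup, but nothing tests whether the indirect effect differs between those subgroups

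*Combined protocol and SAP*

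**What the plan says.** Section C2 lists the moderators and gives their status: "Moderators exploratory and based on prior work; they are: gender, race/ethnicity", followed by nine more, which makes 11 by my count. Section C1 also labels Aim 3e exploratory.

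Section F3 tests each moderator through "three way interactions between time, treatment condition, and each moderator". The next step is "In cases where moderators are significant, we will then conduct mediator analyses separately by subgroups defined by these moderators", and the reason given is "because different intervention effects often imply different mechanisms by which effects are occurring".

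Mediation is tested by structural equation models with "confidence intervals derived from bootstrapping of indirect effects and total effects". One comparison of indirect effects between groups is planned: "Moderated mediation (with treatment vs control as the moderator) will be tested by constraining the indirect effect to be equal across treatment and control groups".

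For the moderator step, F3 gives no alpha, no rule on how many tests count as a trigger, no multiplicity rule, and no rule for forming subgroups from moderators scored on a scale.

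**The concern.** The stated reason for splitting the sample is to learn whether mechanisms differ. That is a question about the difference between two indirect effects. Fitting the mediation model separately in each subgroup gives an interval for each indirect effect but none for the difference. An interval that excludes zero in one subgroup and includes it in the other does not show that the two differ.

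The arm-based equality test in F3 does not fill the gap, because its groups are treatment and control, not moderator categories.

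At stake are secondary, exploratory conclusions. F3 says the moderator work is meant to show who benefits and who may need a differently tailored programme later. A spurious mechanism in one subgroup could misdirect that work.

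**Working it through.** **The plan's own figure.** F1 reports Monte Carlo power above 80% for secondary outcomes, with 0.2 for each moderation effect and about 3,154 + 3,154 = 6,308 completers. The simulation cannot be rebuilt, because alpha, intraclass correlation, variances and base rates are not given. An approximate check (SD 1, two-sided 0.05, 1:1 arms, no clustering, binary moderator with share q) uses SE = √(4/(Nq) + 4/(N(1−q))):
- q = 0.5: SE 0.0504, power 0.98
- q = 0.2: SE 0.0630, power 0.89
- q = 0.1: SE 0.0839, power 0.66

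The stated bound is plausible except for a very uneven moderator. F1 gives no false-positive figure for this step.

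**Step 1: false triggers.** Assume alpha 0.05, independent moderators and no true moderation. P(at least one) = 1 − 0.95^k.
- k = 11 (one test per moderator): 1 − 0.95^11 = 43.1%
- k = 33 (11 × 3 follow-ups, all independent): 1 − 0.95^33 = 81.6%
- 11 × 3 with time-point tests correlated 0.9 to 0.3 (simulated): 62% to 80%

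The chance passes one half at k = 14 (51.2%; k = 13 gives 48.7%). These rates are for one outcome.

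**Step 2: from trigger to discordant mediation.** Suppose the truth is the same in two subgroups and each subgroup test is positive with probability p. One mediator is discordant with probability 2p(1−p); at least one of m is discordant with probability 1 − (1 − 2p(1−p))^m. The plan names eight mediators by my count: dysfunctional cognitions, CBT skills, avoidance, behavioral activation, restraint, weight/shape concerns, early engagement and rapid response. Some are disorder-specific, so eight is an upper count and m = 2 is shown for contrast.

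| p | m = 2 | m = 8 |
|---|---|---|
| 0.05 | 18% | 55% |
| 0.50 | 75% | 99.6% |
| 0.80 | 54% | 95% |
| 0.99 | 4% | 15% |

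Discordance is most likely at middling power and rare at very high power.

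**Step 3: both steps together.** Simulation with 11 irrelevant binary moderators, eight independent mediators, time-point correlation 0.5, a joint-significance test in place of the bootstrap interval, and trigger and mediation estimates drawn independently. The table gives the share of trials with a false trigger followed by at least one discordant mediator, N = 6,308.

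| Treatment–mediator / mediator–outcome path | Split | One test per moderator | Three time points |
|---|---|---|---|
| 0 / 0 | 50/50 | 2% | 6% |
| 0 / 0.2 | 50/50 | 25% | 56% |
| 0.05 / 0.2 | 50/50 | 44% | 75% |
| 0.1 / 0.2 | 20/80 | 46% | 77% |
| 0.2 / 0.2 | 50/50 | 0.3% | 0.3% |
| 0.2 / 0.2 | 20/80 | 19% | 39% |

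With N = 3,154 (one severity stratum), 0.2 / 0.2 paths and equal halves, the figures are 15% and 33%. The simulated single-test trigger rate ran from 41% to 46% around the exact 43.1%, so the entries carry noise of a few points.

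**Step 4: does a formal test cure it?** Eight separate between-subgroup tests at 0.05 have a family-wise error of up to 1 − 0.95^8 = 33.7%. Following a 0.05 trigger on 11 moderators, and treating trigger and test as independent, this gives 1 − (1 − 0.05 × 0.337)^11 = 17%. The simulation gave 13-19% with one trigger test per moderator and 31-38% with three time points, where the mediator–outcome path was 0.2. One test per moderator that covers all mediators together would give 1 − (1 − 0.05 × 0.05)^11 = 2.7% on the same assumptions.

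**The case against.** The strongest reply has four parts.

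- **The subgroups are compared.** The trigger is itself an interaction test that treatment effects differ. This stands: it would be wrong to say that the plan has no test of subgroup differences. The missing test is of the indirect effect.
- **The aim is exploratory.** Moderators are so labelled in C1 and C2, and F3 nowhere says that significance in one subgroup only will be reported as a different mechanism. This also stands. It lowers the weight of any finding but does not supply the comparison for which the split is made.
- **The rates rest on assumptions.** No alpha is stated, time-point tests are correlated, and several moderators probably correlate too. F3 does not say that each time point is a separate trigger. Hence a range is given, and 82% is its upper end for one outcome.
- **Subgroups may not need new cut-points.** Symptom severity already has high-risk and clinical categories in Table 3. That is true for severity. For scales such as motivation or cognitive distortion no rule is given.

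A reader might infer that chance alone will usually produce claims of different mechanisms. The documents do not support that. With one test per moderator and one outcome, a false trigger occurs in fewer than half of trials. At the plan's own 0.2 paths with equal halves, almost none lead to discordant results.

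**Conclusion.** The gap is real and limited: subgroup mediation is used to look for different mechanisms without a test that the indirect effects differ. With alpha 0.05, independent moderators and no true moderation, at least one false trigger is expected in about 43% of trials, or about 62-82% if three time points each count. The chance that a discordant mediation result follows runs end to end from 0.3% to 77% at N = 6,308 (up to 79% at N = 3,154). It is worst when the intervention moves its targets weakly and the mediator still predicts outcome. These figures also assume binary moderators, independent mediators and no clustering. The point is a cheap improvement to an exploratory aim and does not touch the primary analysis.

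**What to change.** In section F3, replace the trigger rule as follows.

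1. Use one joint time-by-treatment-by-moderator test per moderator: 3 df for a binary moderator or a continuous one entered linearly, 3(k−1) df for k categories such as race/ethnicity or presenting disorder. For quality of life, which the E2 schedule does not collect at 6 weeks, use 2 and 2(k−1).
2. For a moderator that passes, test in the full sample whether the indirect effect differs. Extend the existing equality-constraint chi-square to moderator categories, or fit moderator-by-path interactions for continuous moderators without cutting them. Test the mediators jointly first, or adjust across them, because eight unadjusted tests leave the error shown in Step 4.
3. Present subgroup mediation as evidence of different mechanisms only if that test supports it.
4. State the alpha and the outcomes covered, and report the number of moderator tests run or a false-discovery-adjusted result alongside.

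Which adjustment to use for an exploratory aim is a matter of preference. As a gauge, Bonferroni over 11 moderators lowers the false-trigger rate from 43.1% to 1 − (1 − 0.05/11)^11 = 4.9%.

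The cost is SAP wording, with the same data and software. Fewer leads will pass, and adjustment reduces power further for uneven moderators, where unadjusted power is already about 0.66 at a 10/90 split.

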### ***E2 Schedule of Measurements***

Participants will be assessed at screening, baseline, 6 weeks, 6 months, and 2 years. All surveys will be administered via Qualtrics. Participants will be compensated by receiving an electronic gift card for completing the Baseline (\$5), 6 week (\$5), 6 month (\$10), and 2-year (\$20) follow-up assessments. Participants will be entered into a sweepstakes to win one of five \$50 gift cards after completing the Baseline, 6 week, 6 month, and 2-year surveys. In addition, once participants complete all four surveys, they will be entered into a sweepstakes to win one of ten \$100 gift cards.

---

All students who receive a recruitment email will be automatically entered into a sweepstakes for one of 40 \$100 electronic gift card prizes.

See table below for schedule of assessments:

	Baseline Screen	Intervention Period	Post-Screen Assessments			Primary Purpose
			6 wks	6 mos	2 yrs	
PARTICIPANTS						
Demographics	x					Mod
Expectancy/credibility	x					Mod
Degree of cognitive distortion	x					Mod
Anxiety: Generalized anxiety; social phobia; panic	x		x	x	x	TO/Mod (symptom severity; comorbidity)
Depression	x		x	x	x	TO/Mod (symptom severity; comorbidity)
Eating disorders	x		x	x	x	TO/Mod (symptom severity; comorbidity)
Chronicity	x					Mod
Comorbidities: Trauma; insomnia; substance use	x			x	x	Mod
Impairment/quality of life	x			x	x	TO/Mod
Motivation for treatment	x		x	x	x	Mod
Mental health treatment utilization	x		x	x	x	TO
Academic impairment (obtained from colleges)	x			x	x	TO
Target engagement Transdiagnostic : dysfunctional cognitions; CBT skills Disorder-specific : avoidance; behavioral activation; restraint; weight/shape concerns	x		x			Med
Early engagement			x			Med
Rapid response			x			Med
Screening and treatment feedback				x	x	--
TREATMENT PROCESS (INTERVENTION CONDITION)						
Mobile treatment process (e.g., sessions completed, messages with coach)		x				Pred
Fidelity/personalization of coaching (i.e., user perception and coder ratings)		x	x	x		Pred
STUDENT MENTAL HEALTH SERVICES CENTERS						
Attitudes toward mobile mental health platform	x					--
Perceptions of mobile mental health platform				x		--
Intended adoption					x	--
Mental health service utilization	x				x	TO

Notes: Light gray shading = occurring during intervention period. Mod = moderator; TO = treatment outcome; Med = mediator; Pred = predictor.

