## **F Statistical Plan**

### ***F1 Sample Size Determination and Power***

Sample size was based on achieving greater than 80% power to detect minimally meaningful differences in primary and secondary outcomes. We will include 20 colleges with approximately equal numbers of participants per campus, and approximately 3,154 high risk and 3,154 clinical participants with complete follow-up data. All power estimates were derived from Monte Carlo simulations (a gold standard in power estimation). For all analyses, power estimation is based on an effect size of .2 (i.e., for the primary

---

outcome, a differential change of .2 in the treatment vs. control group; for moderator analyses, effect size was .2 for each moderation effect; for mediator analyses, each pathway within the mediation was estimated at .2). We thus have power to detect smaller differences than we anticipate based on assumptions; this extra power is important, given that smaller differences would still be clinically meaningful at a population scale, particularly considering the modest cost of this online intervention. Power for all secondary outcomes was also estimated within the Monte Carlo simulation using all moderators within the same model; and all mediators within the same model targeting a .2 effect size, reflecting a conservative approach to power calculation and model estimation. Results of the Monte Carlo simulations suggested we had greater than 90% power to detect all primary outcomes and greater than 80% power to detect all secondary outcomes.

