## ***F3 Analysis Plan***

To evaluate efficacy of the mHealth platform vs. usual care, in engaging participants (Aim 1) we will use hierarchical logistic regression to examine uptake (i.e., individuals beginning any sort of treatment). Outcome will be at least one session of mental health services use (either online or in-person) assessed at 6 weeks, 6 months, and 2 years. Using hierarchical logistic regression, we will also examine efficacy in reducing or preventing number of students with mental health disorders (i.e., a positive screen for at least one of anxiety, depression, or ED as the outcome reflecting a "clinical case") assessed at 6 weeks, 6 months and 2 years, with a primary endpoint of 2 years. This allows for a single, universal outcome applicable to everyone in the study. Both logistic regression models will include random intercepts for colleges and for students nested within colleges, and account for repeated assessments within students, and will estimate the following fixed effects: main effect of time (coded as a factor variable, including baseline, 6-weeks, 6-months, and 2 years), treatment condition, and two-way interaction between time and treatment condition.

To evaluate reduction in disorder-specific symptoms (Aim 2b) and improvement in quality of life (Aim 2c), multilevel models will be used. Analyses of symptom change will be conducted within each clinical disorder subgroup separately with relevant symptoms as the response variables. We will also use a z-score to standardize primary symptom measures to obtain an estimate for a unified intervention effect. All symptom models will include random intercepts for colleges and for students nested within colleges, account for repeated assessments within students, and will estimate the following fixed effects: main effect of time, treatment condition, and two-way interaction between time and treatment condition. Parameter estimates from these models will allow separately

---

comparing change between arms from pre to 6 weeks, pre to 6 months, and from pre to 2-year follow-up. Each model will use dummy-coded factor terms as a stringent test of the treatment to ensure that: 1) treatment was associated with significantly greater change from pre to post than the control group; and 2) gains made in treatment at 6 weeks are maintained and significantly greater than baseline at each follow-up.

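### Aim 3e tests baseline severity and impairment as moderators while the same baseline values are also the first response, so the baseline-referenced three-way term can be inestimable (caseness) or have a wrong standard error (scores)

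*Combined protocol and SAP*

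**What the plan says.** C2 lists symptom severity, comorbidity and impairment among the moderators. The table in E2 tags the anxiety, depression and eating-disorder measures "TO/Mod (symptom severity; comorbidity", and impairment/quality of life likewise as both outcome and moderator. All are taken at baseline and again at follow-up.

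In F3, the logistic models for uptake and caseness have time "coded as a factor variable, including baseline, 6-weeks, 6-months, and 2 years". The symptom and quality-of-life models are set up for "comparing change between arms from pre to 6 weeks, pre to 6 months, and from pre to 2-year follow-up". Baseline is therefore part of the response in both families.

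For Aim 3e, F3 adds all two-way terms and "three way interactions between time, treatment condition, and each moderator", with a random effect of time within student and campus intercepts. That paragraph does not name the outcome, restate the levels of time or say how severity is coded. Nothing in the plan removes baseline from the response when the moderator is the baseline value of that outcome.

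Table 3 splits entrants into those clinical for at least one condition and those at high risk with no clinical condition. F1 sizes the trial on the same split: "approximately 3,154 high risk and 3,154 clinical participants with complete follow-up data".

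**The concern.** When the moderator is the baseline value of the outcome, or determines it, the baseline response carries no random variation given the moderator. A three-way term that measures change from baseline then uses a cell that is fixed by design.

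For caseness this can be complete separation, which a larger sample does not cure. Software may still print a number, so the fault could pass unnoticed. For scores, the baseline residual is exactly zero, while the model's covariance structure implies that it varies.

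F3 uses these tests to pick out subgroups that benefit most, and a significant moderator leads to separate mediator analyses by subgroup. A meaningless or miscalibrated test would therefore decide which further analyses are run.

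**Working it through.** **Plan's own figure.** The plan gives no standard error for this test. F1 states more than 80% power for secondary outcomes, with an effect of .2 for each moderation term. A simple check uses a binary moderator and 3,154/2 = 1,577 students per arm and stratum (1:1 allocation and two-sided 5% are assumptions). The SE is √(4/1577) = 0.0504, so power is Φ(0.2/0.0504 − 1.96) = 97.8%. This agrees with the claim but does not reproduce it, because the simulation inputs are not given.

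**Caseness, severity coded as entry status.** Assumed 2-year caseness is .25 (high risk) and .55 (clinical) in control, and .20 and .50 in the treated arm. There are 1,577 students per cell, and the logistic model has no random effects.

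- Each cell contributes 1/[n p(1−p)] to the variance.
- The 2-year cells give 0.00338 + 0.00396 + 0.00256 + 0.00254 = 0.01244.
- The three-way variance adds four baseline cells, where the fitted p tends to 0 or 1. After 8 Newton iterations the baseline logits are about ±9.2, so each cell adds about 6.29, and the SE is √(4 × 6.29 + 0.012) = 5.0.
- Each further iteration moves the logits by about 1, so the SE grows by a factor of about e^0.5. It is 14 at 10 iterations, 166 at 15 and 2,024 at 20.
- The 2-year treatment-by-severity contrast (two-way term plus 2-year three-way term) cancels the baseline cells. Its SE is √0.01244 = 0.112 at every iteration.

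A random-intercept logistic fit to simulated data (assumed student SD 1.5) shows the same. The three-way term can be −0.057 or −3.057 at the same log-likelihood of −11731.960. Fitting follow-up visits only gives −0.057 with SE 0.144.

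**Caseness, other codings.** These were checked on simulated entrants.

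| Coding of severity | Separation at baseline | SE of baseline treatment × severity |
|---|---|---|
| Entry clinical / high risk | complete | none |
| Worst-disorder score | complete | none |
| Count of clinical disorders | complete | none |
| One disorder's caseness, own scale | complete | none |
| One scale, three-disorder caseness | no | 0.077 |
| Three scales entered linearly | no | 0.100 |
| Mean z-score | no | 0.209 |
| Index-disorder score | no | 0.414 |

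The SEs are on different scales and only show that they are finite.

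**Score moderated by its own baseline.** Assume follow-up residuals with equal variance v and correlation ρ. The baseline residual is 0.

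- The true variance of the visit-minus-baseline term is proportional to v.
- A random-intercept model averages over four visits. Mean variance is 3v/4 and mean covariance is ρv/2, so the model variance is 2(3/4 − ρ/2)v = (1.5 − ρ)v.
- True SE / model SE = 1/√(1.5 − ρ), which is 0.91 at ρ = .3, 1.00 at .5, 1.12 at .7 and 1.20 at .8. Type I error at a nominal 5% is 3.2%, 5.0%, 8.0% and 10.1%.
- E2 does not schedule quality of life at 6 weeks, so it has three responses. The model variance is then (4 − 2ρ)v/3 and the ratio is 0.94 at ρ = .3, 1.00 at .5 and 1.12 at .8.
- With a random slope added and four visits, the best-fitting covariance gives ratios from 0.84 (2 years, ρ = .3) to 1.41 (6 weeks, ρ = .8), with time scored by visit number.

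**The case against.** The strongest reply has four parts.

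1. **The Aim 3e paragraph does not restate outcomes or time levels, and its random effects differ from those of the Aim 1 and 2 models.** F3 also describes caseness as assessed at the three follow-ups. This stands as a gap in the text. However, the same section makes baseline a level of the time factor for that outcome, and carrying this over is the natural reading.

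2. **Entry status is not on C2's list of moderators.** It appears as a screening and sample-size split. This stands: the divergence depends on a coding that the plan leaves open, and four plausible codings avoid it.

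3. **The information is not lost.** This stands. A reader might infer that moderation by severity cannot be tested at all for caseness. It can: the 2-year contrast is available from the same fit. What fails is the baseline-referenced term that the plan names.

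4. **A random effect of time lets the variance differ by visit.** This is true, but it does not reproduce a zero baseline variance. It changes the ratio without removing the error. A reader might also infer that the intervals are always wrong. They are not: with a random intercept the ratio is 1 at ρ = .5, and the zero residual requires the same scale entered linearly.

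C1 and C2 both label the moderator work exploratory, which limits the weight of the point.

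**Conclusion.** The point holds in a conditional form. Read with the outcomes and time levels given earlier in F3, the Aim 3e models place the same baseline value on both sides.

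For caseness, any coding of severity that fixes case status at entry leaves the baseline-referenced three-way term without a finite standard error. Other codings do not. For scores, the SE of that term is off by a true/model ratio of about 0.84 to 1.41, in either direction, and can be about right. These figures rest on an assumed follow-up correlation of .3 to .8, equal follow-up variances, and a random intercept with or without a slope. The documents give none of these.

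The treatment comparisons in Aims 1 and 2 do not use these moderators and are not affected. The consequence is confined to exploratory moderator findings and to the subgroup mediator analyses that they trigger. That is enough to justify correcting the wording before analysis.

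**What to change.** In F3 (Aim 3e), define how severity is coded and name the outcomes of the moderation models. Then add a rule for any moderator that is, or determines, the baseline value of the outcome: symptom severity, entry clinical/high-risk status, number of the three target disorders, and baseline impairment.

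For these, model only the 6-week, 6-month and 2-year responses (6-month and 2-year for quality of life), with the baseline value as covariate. Test treatment by moderator at each visit, with 2 years as the main test. Trauma, insomnia and substance use are outside the rule, because they neither equal nor define the outcome.

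The cost is SAP wording only. No new data are needed, and baseline is still used as a covariate.
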